#### 7.4.2.5 Use of Immunomodulatory Agents

The rate of use of immunomodulatory agents as treatment for COVID-19 will be compared between treatment arms using the CMH test stratified by age (< 60 years versus  $\geq 60$  years) and baseline 7-point clinical status scale (baseline 3 or 4 versus 5). The point estimates and 95% confidence intervals of the rates of immunomodulatory agents use will be presented by treatment arm. The CMH odds ratio, difference in rates of immunomodulatory agent use, and associated 95% confidence intervals will be presented.

In addition, the number of immunomodulatory agents will be summarized using descriptive statistics (e.g. number of immunomodulatory agents used per patient). Additional summaries presenting the percentage of patients using immunomodulatory agents in each defined category in [Appendix 1](#) and the immunomodulatory agents summarized by preferred term may be generated.

Immunomodulatory agents used will be listed by patient.

### **7.4.3 Tertiary Analyses**

#### **7.4.3.1 Markers of Disease Severity**

Markers of disease severity will be summarized with descriptive statistics. The summary will include both recorded values and change from baseline for each scheduled assessment and maximum and minimum post-baseline assessment. Both scheduled and unscheduled visits will be considered in derivations of the maximum and minimum post-baseline assessments.

Markers of disease severity data will be listed by patient.

## **7.5 Safety Analyses**

Safety will be assessed through 30 days of follow-up after the last dose of study treatment and assessed by the cumulative incidence, severity and seriousness of TEAEs, drug discontinuations, laboratory values, and clinical assessments.

Summaries will be tabulated by treatment arm and in total for the Safety Population.

### **7.5.1 Adverse Events**

Summaries of adverse events will be presented by treatment arm and in total for the Safety Population.

An overview of treatment-emergent adverse events will be provided which summarizes the patient incidence of the following for the Safety Population. This overview will include the number and percentage of patients with:

- Any TEAEs,
- TEAEs related to study treatment,
- Serious TEAEs (TESAEs),
- CTCAE Grade 3+ TEAEs,
- TEAEs with outcome of death,
- TEAEs leading to study drug discontinuation, interruption, or dose reduction,
- Cardiac TEAEs (defined by MedDRA SMQ List),

- Haemorrhage TEAEs (defined by MedDRA SMQ List),

The number and percentage of patients with TEAEs will be tabulated by the highest CTCAE Grade, System Organ Class, and Preferred Term (PT).

In addition, serious TEAEs (TESAEs), CTCAE grade 3 or more TEAEs, TEAEs leading to study drug discontinuation, interruption, or dose reduction, TEAEs with an outcome of death, and related TEAEs will be summarized by System Organ Class and PT.

The PT of TEAEs of all grades and grade 3 or more TEAEs will also be presented for each treatment arm in order of decreasing frequency.

Cardiac and haemorrhage TEAEs will also be summarized by System Organ Class and PT.

For all above summaries, patients with multiple adverse events will be counted only once per System Organ Class and PT.

Listings of all AEs (i.e. including those that are not treatment-emergent), SAEs, AEs leading to treatment discontinuation, AEs leading to treatment interruption or dose reduction, AEs with outcome of death, Cardiac TEAEs, and Haemorrhage TEAEs will be provided.

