### **11.1.2 Safety Endpoints**

Safety will be assessed through 30 days of follow-up after the last dose of study treatment and assessed by the cumulative incidence, severity and seriousness of TEAEs, drug discontinuations, laboratory values, and clinical assessments.

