## **11.4 Safety Analysis**

All safety analyses will be performed on the Safety population.

Safety will be assessed through 30 days of follow-up after the last dose of study treatment and assessed by the cumulative incidence, severity and seriousness of TEAEs, drug discontinuations, laboratory values, and clinical assessments.

TEAEs will be coded using MedDRA and summarized by SOC, PT, and treatment arm as the number and percentage of patients with an event. The following subsets of TEAEs will also be summarized by treatment arm: AEs related to study treatment, AEs by CTCAE v4.03 grade, AEs leading to treatment discontinuation, and SAEs.

Clinical laboratory data will be assigned a CTCAE v4.03 grade and summarized with descriptive statistics and, where possible, in shift tables comparing the worst post-baseline shift relative to baseline.

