### 5.2.1 Adverse Events

An AE is any untoward medical occurrence in a patient or clinical investigation patient administered a pharmaceutical product and that does not necessarily have to have a causal relationship with this treatment.

AEs will be collected during the clinical study from the time of randomization through 30 days following the last dose of pacritinib/placebo. AEs that occur after the 30-Day Post EOT Visit that are considered possibly related to pacritinib/placebo or procedure should also be recorded. For screened patients who are not randomized, only SAEs occurring between the time of informed consent and determination of screen failure are reported.

The following information should be captured for all AEs: date of onset and resolution, severity per Common Terminology Criteria for Adverse Events (CTCAE), seriousness, the investigator's assessment of relationship to pacritinib/placebo, event outcome, and action taken with study medication due to the reported event. If concomitant treatment is given for the AE, this information should be captured on the appropriate electronic case report form (eCRF). If an AE results in early termination of the patient's pacritinib/placebo treatment period, "AE" should be selected as the reason for discontinuation on the eCRF.

The CTCAE version 4.03 will be used for the grading of adverse events.

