### 7.1 General Statistical Considerations

Unless specified otherwise, the analyses of data collected will be descriptive and summaries will be presented separately for each treatment arm and in total for the specified analysis population. Statistical analyses will be descriptive and no formal hypothesis testing or comparative analyses between treatment arms will be performed unless stated. Confidence intervals (CIs) will be constructed at the 95% confidence level where appropriate. For categorical variables, confidence intervals will be calculated using the Clopper-Pearson method where appropriate.

For continuous variables, the number of observations (n), mean, standard deviation, median, q1, q3, minimum, and maximum will be provided as summary statistics. For categorical variables, the frequency and percentage in each category will be displayed.

Summary tables will in general display 2 treatment arms:

- Pacritinib 400 mg
- Placebo

A total column will be added for table summaries if appropriate.

Efficacy analyses will in general be based on the ITT Population according to the randomized (planned) treatment arm.

Safety analyses will in general be performed using the Safety Population according to the treatment actually received.

Subject disposition, demographics, and clinical baseline characteristics data will be summarized for the ITT Population. If the ITT Population differs from other defined analysis populations, additional patient characteristic summaries may be generated using other analysis populations.

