## **7.2 Study Population Data**

### **7.2.1 Patient Disposition**

Patient disposition will be summarized using counts and percentages for the ITT Population.

The following patient disposition categories will be summarized:

- Patients screened;
- Patients randomized;
- Patients who received study treatment;
- Patients that completed planned study treatment;
- Patients discontinued from study treatment;
- Patients that completed the study;
- Patients who discontinued the study.

For patients who discontinued study treatment and patients who discontinued the study, reason for discontinuation will be provided.

The total number of patients in each defined analysis population will be tabulated.

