## **9 CHANGES FROM PROTOCOL-SPECIFIED ANALYSIS**

No changes from the protocol-specified analysis are planned.

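### SAP 7.5.1 puts adverse events that end study drug in one item with those that only interrupt it or reduce the dose, and does not specify the separate by-arm discontinuation summary listed in Protocol 11.4

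*SAP*

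**What the plan says.** Protocol section 11.4 names the subsets of treatment-emergent adverse events (TEAEs) to be summarised by treatment arm in the Safety population: "AEs related to study treatment, AEs by CTCAE v4.03 grade, AEs leading to treatment discontinuation, and SAEs". Discontinuation stands alone there, and interruption and dose reduction are not on the list. Protocol section 11.1.2 also counts "drug discontinuations, laboratory values, and clinical assessments" among the measures by which safety is assessed.

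SAP section 7.5.1 words the item differently. Its overview of patient incidence has one bullet, "TEAEs leading to study drug discontinuation, interruption, or dose reduction". The same phrase returns as one entry in the sentence on summaries by System Organ Class and preferred term. The section's closing sentence on listings does make a split: "AEs leading to treatment discontinuation, AEs leading to treatment interruption or dose reduction".

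Two other parts of the SAP bear on the point. Section 7.2.1 (Patient Disposition, ITT population) says: "For patients who discontinued study treatment and patients who discontinued the study, reason for discontinuation will be provided". Section 7.3 (Exposure, Safety population) summarises dose modifications by arm, with reasons. SAP section 9 states: "No changes from the protocol-specified analysis are planned".

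**The concern.** A permanent stop and a temporary hold are different outcomes. Under Protocol Table 3, a treatment-related grade 2 bleed leads to a hold of up to 2 days and a restart at the same dose, whereas a grade 4 bleed ends treatment. Holds for thrombocytopenia, diarrhoea and other toxicities may last up to 7 days (Protocol Tables 3, 5 and 6). In the SAP's item, patients with any of these courses count alike.

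Secondary objective 7 is the toxicity profile of pacritinib. A reader of the study report will want to know whether more patients on pacritinib had to stop for an adverse event, and which events were responsible. A combined row and a combined System Organ Class and preferred-term table do not answer either question. Someone programming from SAP 7.5.1 could deliver exactly what it says and still not deliver the subset listed in Protocol 11.4, with no deviation on record.

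**Working it through.** **Step 1. Which table would show permanent stops due to adverse events?**

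| Source | Discontinuation alone? | By arm? | Population | By event? |
|---|---|---|---|---|
| Protocol 11.4 | Yes | Yes | Safety | Not stated for the subsets |
| SAP 7.5.1 overview | No, listed with interruption and reduction | Yes | Safety | No |
| SAP 7.5.1 System Organ Class/preferred term | No, same item | Yes | Safety | Yes |
| SAP 7.5.1 listings | Yes | No, patient-level | Not stated | Yes |
| SAP 7.2.1 disposition | Yes, as a reason for stopping drug | Yes, by default | ITT | No |
| SAP 7.3 exposure | No, any dose modification and its reasons | Yes | Safety | No |

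The disposition entry rests on two further statements. SAP 5.2.1 says that when an adverse event ends treatment early, AE "should be selected as the reason for discontinuation on the eCRF". SAP 7.1 sets the default that "summaries will be presented separately for each treatment arm and in total for the specified analysis population". Together they mean that the by-arm count survives. No row of the table combines discontinuation alone, by arm, in the Safety population, and none gives discontinuation by arm and by event in any population.

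**Step 2. Can the split be made from the data collected?** Protocol 8.1.3.4 codes the action taken as, among others, dosage reduced, drug interrupted and resumed at the same dose, or drug withdrawn. These are separate codes, so it can.

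**Step 3. What does a combined row do to a difference in permanent stops?** The documents give no rates of discontinuation or holds for this trial, so there is no stated figure to reproduce. The counts below are assumptions, with about 100 per arm from the planned 200 at 1:1 and each patient counted once.

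Let d be the proportion who stop permanently and h the proportion with a hold or reduction only, with subscript 1 for pacritinib and 0 for placebo.

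- Combined difference = (d1 − d0) + (h1 − h0)
- Combined ratio = (d1 + h1) / (d0 + h0)
- 95% interval = difference ± 1.96 × √[p1(1 − p1)/100 + p0(1 − p0)/100], where p = d + h

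For discontinuation alone at 12 versus 4, the standard error is √(0.001056 + 0.000384) = 0.0379, so the interval is 8 ± 7.4 points.

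| Hold-only patients added (pacritinib, placebo) | Row shown | Difference, points (95% interval) | Ratio |
|---|---|---|---|
| none: discontinuation alone | 12 v 4 | 8 (0.6 to 15.4) | 3.00 |
| 10, 10 | 22 v 14 | 8 (−2.6 to 18.6) | 1.57 |
| 15, 15 | 27 v 19 | 8 (−3.6 to 19.6) | 1.42 |
| 25, 25 | 37 v 29 | 8 (−5.0 to 21.0) | 1.28 |
| 20, 10 | 32 v 14 | 18 (6.6 to 29.4) | 2.29 |
| 10, 18 | 22 v 22 | 0 (−11.5 to 11.5) | 1.00 |

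With equal holds the absolute difference is preserved, the ratio moves towards 1 and the interval widens. With more holds on pacritinib the combined difference grows. It vanishes only if placebo has an excess of holds that matches the excess of stops on pacritinib. In every unequal case the row no longer measures permanent stops.

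**The case against.** Four points can be made for the SAP.

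*Pooling is inferred.* The bullet does not say that the three actions are combined. It could be programmed as three rows, and SAP 8.2 leaves table formats to a separate specification. This stands in part. But the other overview bullets each name one category, and the same section splits the actions when it turns to listings. One combined row is the natural reading, and nothing in the text rules it out.

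*The information is not lost.* A reader might infer that the trial will have no count of discontinuations due to adverse events. The documents do not support that: disposition gives the count by arm, the listings identify the events, and SAP 7.5 repeats drug discontinuations as a safety measure to be tabulated by arm. What remains missing is narrower: a specified Safety-population summary of stops due to adverse events, and any by-arm breakdown of those stops by event.

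*The protocol does not clearly ask for the breakdown.* Protocol 11.4 asks for the subsets by treatment arm and does not expressly require System Organ Class and preferred-term tables for each. This stands. The separate row is the protocol item; the separate table is good practice.

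*Holds need not mask toxicity.* A reader might infer that holds, being commoner in deteriorating placebo patients, would cancel a pacritinib signal. The documents point more the other way. Protocol 8.1.1 keeps progressive disease and its signs and symptoms out of adverse event reporting. Protocol 6.5.2 confines dose modification rules to treatment-related events and QTcF prolongation, and it names the main triggers as effects already associated with pacritinib. An excess of such holds on pacritinib is therefore more plausible. Cancellation remains arithmetically possible but is not the expected case.

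**Conclusion.** The point holds as a gap in safety reporting. Read naturally, SAP 7.5.1 replaces a subset listed in Protocol 11.4 with a broader composite, and SAP 9 does not declare the difference. Disposition and listings soften the effect but do not supply by-arm, by-event information on permanent stops in the Safety population.

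The supportable consequence is dilution. Under the assumed 12 versus 4 stops and equal holds of 10% to 25% per arm, a threefold ratio reads as 1.57 to 1.28 and the interval around the unchanged 8-point difference widens. Those rates are illustrative. They are not estimates for this trial, and the intervals are not outputs that the plan promises. No formal comparison of adverse events is planned, so no test result or decision rule depends on the choice. The primary endpoint, sample size, power and type I error are unaffected.

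**What to change.** In SAP 7.5.1, replace the combined item in both places with:

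- TEAEs leading to study drug discontinuation: their own overview row and their own System Organ Class and preferred-term table, by arm, Safety population.
- TEAEs leading to interruption or dose reduction: a separate row and table.

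The composite may be kept as an additional row. State that the categories are derived from the action-taken codes, and that a patient with events of both kinds counts once in each row, since the two rows will then not add up to the composite.

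The cost is SAP wording, one extra overview row and one extra table. No new data are needed, and the change brings the SAP back into line with Protocol 11.4, so the statement in SAP 9 would be true on this point.

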### **7.5.2 Laboratory Assessments**

Clinical laboratory evaluations will be summarized using descriptive statistics for all laboratory parameters including absolute measurements and changes from baseline by scheduled time of evaluation. Changes from baseline by scheduled time of evaluation will include last visit on-study, maximum post-treatment value, and minimum post-treatment value. Both scheduled and unscheduled post-treatment visits will be considered for the summaries of the maximum and minimum post-treatment values. Results will be presented in SI units.

Laboratory results will be graded according to NCI-CTCAE version 4.03 as applicable. A shift table, presenting the frequency tabulation for baseline to each timepoint and the worst post-treatment value according to the NCI-CTCAE grade, will be provided for selected clinical laboratory tests. For select parameters (e.g. glucose), separate shift tables indicating hyper- and hypo-directionality of change may be produced. Both scheduled and unscheduled post-treatment visits will be considered in tabulation of the worst post-treatment value.

Clinical laboratory evaluations in SI units will be listed, including high and low flags, CTCAE grades where applicable, and the corresponding normal range.

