### **3 STUDY DESIGN**

This is a Phase 2 randomized, double-blind, placebo-controlled, multicenter study to evaluate the efficacy and safety of pacritinib in hospitalized patients with severe COVID-19 with or without cancer. Severe COVID-19 is defined as confirmed disease in patients who are hospitalized with hypoxia ( $\text{SpO}_2 \leq 93\%$  on room air), respiratory rate  $>30$ ,  $\text{PaO}_2/\text{FiO}_2 <300$ , but do not require IMV.

Patients will be randomized 1:1 to receive pacritinib (400 mg QD on Day 1, then 200 mg BID from Day 2 to Day 14) + SOC or placebo + SOC stratified by age (< 60 years versus  $\geq 60$  years) and the 7-point ordinal scale of clinical status scale (baseline 3 or 4 versus 5). The study duration will be 8 weeks.

Assigned treatment will continue for up to Day 14 or until the patient experiences intolerable adverse events (AEs), withdraws consent, or initiates another investigational therapy, or until the study is terminated. Assigned therapy may be given for an additional 7 days (for a total of 21 days) with the approval of the Medical Monitor if, in the opinion of the investigator, the patient's clinical signs and symptoms are improving and the potential benefit outweighs the potential risk. In the event of hospital discharge, patients will complete treatment with the assigned therapy as an outpatient.

The primary endpoint is the effect of treatment on the proportion of patients who require IMV and/or ECMO or die by Day 28.

The study will be monitored by an IDMC comprising a multidisciplinary group of at least three voting members in the fields of hematology, infectious disease, and biostatistics. Additional personnel may be added to the IDMC at the request of the IDMC membership. The membership, roles, and responsibilities of the IDMC will be fully defined by an IDMC charter.

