Safety will be monitored with physical examinations, clinical laboratory assessments, and electrocardiogram (ECG) monitoring for inpatients. Patients who are discharged from the hospital while still on study will be monitored weekly. Outpatient monitoring will include telephone/videoconference contact and may also include review of the patient's electronic medical record. Laboratory and ECG assessments will not be required for monitoring outpatients, including those completing their course of study drug. Specified pacritinib/placebo dosage modifications will be followed to address identified abnormalities. AE data will be collected from the time of randomization through 30 days following the last dose of pacritinib/placebo. Serious adverse events (SAEs) assessed as related to pacritinib/placebo or study procedure by the investigator or Sponsor shall be followed until the event resolves, stabilizes or the patient is lost to follow-up. SAEs assessed as unrelated to pacritinib/placebo or study procedures shall be followed for 30 days after the last dose of pacritinib/placebo, or until

the event resolves, returns to baseline, stabilizes, or the patient is lost to follow-up, whichever comes first.

At the request of an investigator, and with agreement of the Chief Medical Officer at CTI, the assigned treatment for an individual patient may be unblinded for the purposes of discussing the ongoing care of that patient.

The approximate study duration for each patient will be 8 weeks. The estimated duration of the entire study is approximately 1 year and is subject to increase as patient enrollment increases.

The schedules of study assessments for all patients are provided in [Table 1](#).

[figure not shown]

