#### **7.1.2.2 *Hematology***

Hematology parameters, (CBC, WBC, hemoglobin, hematocrit, and platelet count), will be evaluated at Screening (may be performed within 24 hours prior to the start of Screening) and daily from Days 2 through 28 or EOT, and on the day of hospital discharge. WBC differential will be evaluated at Screening (may be performed within 24 hours prior to the start of Screening), Day 8, Day 15 or EOT, Day 22, Day 28, and on the day of hospital discharge. Hematology tests are not required after hospital discharge. Analysis of CBC results will be performed at local laboratories. Results from unscheduled hematology tests should be entered into the electronic database using an Unscheduled Hematology case report form (CRF). Pacritinib/placebo dosage modifications will be implemented for clinically significant AEs identified with this testing per the guidelines for “Treatment-Related Thrombocytopenia and Bleeding” (Section 6.5.3).

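### The worst-grade laboratory tables make no allowance for monitored time, so a difference in hospital stay between arms would distort the comparison of cytopenias

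*SAP*

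**What the plan says.** **How the tables are built.** SAP 7.5.2 plans "A shift table, presenting the frequency tabulation for baseline to each timepoint and the worst post-treatment value according to the NCI-CTCAE grade" for selected tests. For the worst value, "Both scheduled and unscheduled post-treatment visits will be considered in tabulation of the worst post-treatment value". The same rule covers the extremes: "Both scheduled and unscheduled post-treatment visits will be considered for the summaries of the maximum and minimum post-treatment values". Protocol 11.4 also plans laboratory summaries "in shift tables comparing the worst post-baseline shift relative to baseline". SAP 7.5 presents safety summaries by treatment arm, and SAP 7.1.4 uses recorded values only unless a rule says otherwise.

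**When blood is drawn.** Protocol 7.1.2.2 schedules the blood count "daily from Days 2 through 28 or EOT, and on the day of hospital discharge", and 7.1.2.4 does much the same for chemistry. Liver and coagulation tests are less frequent: Days 8, 15 or EOT, 22 and 28, and the day of discharge.

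**What happens at discharge.** Protocol 7.1.2.2 states "Hematology tests are not required after hospital discharge". Protocol 3 states "In the event of hospital discharge, patients will complete treatment with the assigned therapy as an outpatient" and also "Laboratory and ECG assessments will not be required for monitoring outpatients, including those completing their course of study drug". Unscheduled results are still to be entered in the database if a test is done.

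**The concern.** A worst value depends on how often one looks. For blood counts and chemistry, the scheduled looks follow days in hospital, while exposure to study drug can continue at home. Two patients with the same daily risk of a grade 3 platelet count will show different worst grades if one is discharged on Day 7 and the other on Day 14.

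This need not balance out between arms, because discharge lies close to the hoped-for benefit. For a patient with baseline score 3 or 4, a 2-point improvement means score 1 or 2, which is out of hospital (Protocol 7.1.1.1 and 11.1.1). A drug that works may therefore shorten its own laboratory follow-up. Thrombocytopenia and anemia are recognized effects of pacritinib: 40.7% and 24.1% at 200 mg BID in the earlier myelofibrosis dose-finding study (Protocol 1.2.4). At stake is whether a reader of the worst-grade table can tell a difference in toxicity from a difference in time observed.

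**Working it through.** **Inputs from the documents.** The plan gives no figure for monitoring time, so there is none to reproduce. With daily draws from Day 2, a patient discharged on Day d has d − 1 scheduled draws: 6 for Day 7, 9 for Day 10, 13 for Day 14 and 27 for Day 28. The last figure takes the schedule to Day 28, as in Protocol Table 1. The text of 7.1.2.2 and 7.1.2.4 says Day 28 or EOT, which could end it sooner.

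**Assumed inputs.** Monitored days per arm, and a constant daily risk h of a first graded abnormality that is seen only on monitored days.

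**Formula.** Proportion shown in the table = 1 − (1 − h)^days.

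| Daily risk, pacritinib v placebo | Monitored days | Table shows | Ratio |
|---|---|---|---|
| 1.5% v 1% | 10 v 10 | 1 − 0.985^10 = 14.0% v 1 − 0.99^10 = 9.6% | 1.47 |
| 1.5% v 1% | 8 v 10 | 1 − 0.985^8 = 11.4% v 9.6% | 1.19 |
| 1.5% v 1% | 8 v 12 | 11.4% v 1 − 0.99^12 = 11.4% | 1.00 |
| 1.5% v 1% | 12 v 10 | 1 − 0.985^12 = 16.6% v 9.6% | 1.73 |
| 1% v 1% | 8 v 12 | 1 − 0.99^8 = 7.7% v 11.4% | 0.68 |

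The last row is a false advantage of 3.6 points (11.36% − 7.73%). The fourth row shows the bias reversing when stay is longer on pacritinib.

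**Second set of assumptions.** Take true 14-day risks p, with h = −ln(1 − p)/14 and the observed proportion equal to 1 − exp(−h × days).

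- 20% v 10% (true ratio 2.0): h = 0.01594 v 0.00753. At 7 v 10 days the table shows 10.6% v 7.2%, ratio 1.46. At 5 v 10 days it shows 7.7% v 7.2%, ratio 1.06.
- 15% v 10% (true ratio 1.5): h = 0.01161 v 0.00753. At 7 v 10 days it shows 7.8% v 7.2%, ratio 1.08.

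The excess disappears when the ratio of stays equals the inverse of the hazard ratio: 1/2.12 = 0.47 in the first case and 1/1.54 = 0.65 in the second.

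**Effect of a monitored-time denominator.** If patient-days run to the first event or the last draw, the expected days per patient are (proportion shown)/h. For 8 v 10 days these are 0.1139/0.015 = 7.59 and 0.0956/0.01 = 9.56. The rates are then 11.39/7.59 = 1.5 and 9.56/9.56 = 1.0 per 100 monitored days, and the assumed 1.5-fold risk is recovered. This depends on a constant hazard and on discharge being unrelated to laboratory risk.

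**The case against.** The strongest points on the other side are these.

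- **The worst grade is not the only display.** SAP 7.5.2 also gives values, changes and grade shifts by timepoint, which compare like days. This stands in part: on any day they include only patients still in hospital.
- **Toxicity is judged mainly on adverse events.** SAP 6.3 assesses the toxicity objective chiefly through TEAEs. These are collected after discharge by weekly contact until 30 days after the last dose (Protocol 7.1.4.8), and clinically significant laboratory results count as AEs (Protocol 8.1.1). SAP 7.1 makes analyses descriptive unless stated otherwise, and the IDMC trigger in Protocol 8.4.1 uses treatment-related grade 4 or 5 AEs. This lowers the stakes. It does not close the gap, since a telephone call cannot find a silent platelet fall that nobody measured.
- **The 8 v 12 day example cancels by construction**, because 1.5 × 8 = 12. A 4-day mean difference is also large. If it came only through the 13-point design effect on ventilation, ECMO or death, each averted event would have to save 4/0.13 = 31 monitored days, more than the 27 scheduled. Both points are fair. The 8 v 10 day case is the milder illustration, and it still shows the excess, reduced.
- **Direction is not known.** Death also ends monitoring, so fewer early deaths on pacritinib would lengthen its follow-up. The earlier cytopenia rates come from myelofibrosis patients with low platelets, treated for about 21 weeks, and give no daily risk for this population. This stands.

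A reader might infer that patients have no blood tests at all once home, or that the tables are bound to hide pacritinib's blood toxicity. The documents support neither. Tests are not required after discharge, but unscheduled results are entered. Masking also needs a large difference in stay or a small true excess.

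**Conclusion.** The point holds in conditional form. As written, the worst-grade comparison for blood counts and chemistry confounds toxicity with monitored time, and SAP 7.5.2 has nothing to separate them. By-timepoint shifts and AE collection reduce the problem but do not remove it.

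On the assumed inputs, a 2-day shorter stay on pacritinib shrinks a 1.5-fold daily risk to a ratio of about 1.2. A 4-day shorter stay removes it, or creates a false advantage of 3.6 points where the risks are equal. A longer stay on pacritinib, or fewer early deaths, would exaggerate the excess instead. The documents give no length of stay and no daily hazard, so these figures show scale and are not predictions. The point concerns how a descriptive safety table is read; it does not touch the primary analysis or the sample size.

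**What to change.** In SAP 7.5.2, for blood counts and chemistry:

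1. Keep the full-period worst-grade table, with a footnote that it is not adjusted for monitoring time.
2. Add by arm the monitored patient-days and the number of draws, scheduled and unscheduled.
3. Add by arm the first grade 3 or higher value per 100 monitored patient-days, counting days to that value or to the last draw. Cumulative incidence with follow-up ending at the last draw would serve instead.
4. Optionally, add a worst-grade table for a common early window as a supplement. It should not be the only comparison between arms: Days 2 to 8, for example, cover 7 of the 14 dosing days, would miss later cytopenia, and are still affected by discharge before Day 8.

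The cost is a short SAP change and one or two tables from data already collected, with no change to the visit schedule. Discharge is related to illness and the hazard may not be constant, so the rate reduces the bias without removing it; the text beside the table should say so.
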